Figure 1 charts the study protocol and randomization.

[figure not shown]

Figure 1: Flowchart of the protocol. After consent, the subject is randomized to the order of low and standard of care dose PET/CT. If the patient opts out of the second whole-body sweep, both exams will be performed at 75 min +/- 10 min p.i., otherwise the 1st sweep will be performed at 60 min +/- 10 min, followed by the 2nd at 75 min +/- 10 min.

Sample Size Considerations

The project statistician has calculated a required sample size of 33 evaluable subjects per imaging modality if we assess tracer uptake (FDG) using both a quantitative (SUVmax) and a visual quality assessment. Based on the literature and our preliminary work, we assume that the coefficient of variation (COV) is 12% and the equivalence limit is 10%. With a total sample size of 33 patients we will achieve 80% power in an equivalence test of means using two one-sided tests (TOST) on data from a two-period cross-over design, using an alpha level of 0.025 (0.05/2) after Bonferroni adjustment each system, respectively. We assume a drop-out rate of 10% (4 subjects) which leads to our target population of 37 enrolled subjects per unique sub-study.

Four imaging systems will be utilized in this study:

- Gemini TOF Astonish system from Philips Healthcare Cleveland
- Biograph mCT from Siemens Knoxville
- Discovery PET/CT from General Electric, Milwaukee
- Vereos 128 PET/CT from Philips Healthcare Cleveland (this is the first commercial digital PET detector system)

The subjects imaged at each of the four PET/CT systems will treated as its own sub-study. Each sub-study will follow the same imaging protocol.

We will evaluate four different state of the art PET/CT system in the above defined six sub-studies which then leads to the overall study population estimate of 204 subjects.

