For secondary assessments, we will determine by three independent, blinded readers the image quality for a diagnostic interpretation with a linear 10 cm scale from exceptional to unacceptable. We will use the same approach to assess the diagnostic confidence and occurrence of image artifacts and to allow for any additional comments desired. For the read assessment, each PET/CT exam will be individually assessed in a randomized order. Upon completion of this assessment and after a duration of several weeks, a matched pair assessment will be performed to assess equivalency during a side-by-side comparison using the same assessment scales. If those assessments confirm equivalency, we plan to add a full diagnostic read of each exam separately with blinded dosing information.

For this Phase I study, we believe that performing intra-individual comparisons on the same PET/CT system is the only way to get unconfounded, objective assessment of the equivalency of dose reduction. In case we would find difference between the four different PET/CT systems, different dose reduction schemes might be necessary.

While we cannot evaluate in this trial the equivalency for response assessment of therapy between the low dose and current standard of care dose, we do have at least the ability to evaluate that the difference in FDG uptake between the whole body sweep at 60 min +/- 10 min and 75 min +/- 10 min for the target regions is not impacted by dose. While this is our hypothesis we want to evaluate, we will at the same time gain insight into the intra-individual variability in FDG uptake within such a 15 min +/- 10 min window. The current guidelines recommend that the PET/CT whole body sweep be performed 60 min +/- 10 min post injection, giving a 20 min window to start the whole body sweep [Shankar]. Current clinical practice however is favoring imaging around 75 min p.i. which leads to a considerable number of protocol deviations in clinical trials.

As Imaging Core Laboratory for a large number of trials which include PET imaging, we see that the protocol deviation rate in time post injection is consistently the highest with rates of 15% to 40% depending on protocol, most frequently however in the time frame of 70 to 80 min post injection. By adding this aim to the protocol, we can answer another burning clinical/scientific question without adding any additional radiation exposure to the patient.

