All paper and electronic data/information will be coded prior to any review or analysis. All paper documents will be stored in a locked file cabinet with limited access in the Department of Radiology at The Ohio State University. All electronic data obtained through PACS or IHIS will be stored in a coded manner on password protected servers with limited access in the Department of Radiology at The Ohio State University. No individual identities will be used in any publications resulting from this study. Officials from examining bodies such as the U.S. Food and Drug Administration or NIH may inspect records pertaining to this study.

Internal Validity

This crossover design is necessary to blind the patient and the technologist to be unbiased during the performance of the imaging, as motion artifacts, positioning, and other aspects can influence image quality to some extent.

Data Analysis

Our primary hypothesis is that the SUVmax will be equivalent between standard of care dosing (13 mCi) and the low dose (5 mCi) in each PET/CT system. The two one-sided tests procedure (TOST) will be used to test the equivalence of SUVmax at 75 min post injection between the standard care of dosing and the low dose. As SUVmax is known to have lognormal distribution, the data will be log-transformed before all analysis. Holm-Bonferroni method will be used to adjust for multiple ROIs. The McNemar-Bowker's test will be used to evaluate the inter-reader reliability in image quality measured from 1-10 scale between every two readers. The average scores will be calculated among those 3 readers. The TOST test will be used to

test the equivalence in the average score of image quality between the standard care of dosing and the low dose.

The percentage of change in SUVmax measured from 60 min to 75 min will be tested first for equivalence between the standard of care dosing and the low dose target ROI in each PET/CT system. Then the SUVmax measured at 60 min will be compared to SUVmax measured at 75 min within standard care of dosing and the low dosing groups, respectively.

V. Bibliography

- 3. Miletich, RS. Positron emission tomography for neurologists. *Neurol Clin.* Feb 2009;27(1):61-88.

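### The McNemar-Bowker test named for inter-reader reliability tests symmetry between readers, not agreement, and no agreement measure is planned

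*Protocol*

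**What the plan says.** The protocol, section IV, Measurement / Instrumentation, makes the reader assessment secondary: "For secondary assessments, we will determine by three independent, blinded readers the image quality". The instrument there is a "image quality for a diagnostic interpretation with a linear 10 cm scale from exceptional to unacceptable" and, at the first reading stage, "each PET/CT exam will be individually assessed in a randomized order".

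The Data Analysis section then sets the method: "The McNemar-Bowker's test will be used to evaluate the inter-reader reliability in image quality measured from 1-10 scale between every two readers". It continues: "The average scores will be calculated among those 3 readers". A TOST on that average is used to "test the equivalence in the average score of image quality between the standard care of dosing and the low dose".

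No kappa, intraclass correlation coefficient (ICC), limits of agreement or other agreement measure appears in the protocol. It sets no criterion for acceptable reliability, and no later step is made conditional on the Bowker result.

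**The concern.** Reliability between readers means that they give the same exam the same, or nearly the same, score. The Bowker null hypothesis is that the probability of (reader 1 = i, reader 2 = j) equals the probability of (reader 1 = j, reader 2 = i) for every pair of categories. Two readers scoring at random from the same distribution satisfy it exactly. So do two readers who agree almost perfectly. The test therefore cannot separate the two situations that a reliability analysis exists to separate.

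At stake is the reported reliability of the image-quality scores. The three readers are averaged and the average is tested for dose equivalence, yet the planned analysis would not show how well the averaged scores agree.

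**Working it through.** **Inputs from the protocol.** Three readers, hence three reader pairs. A scale written as 1-10 in Data Analysis, which gives 10 x 9 / 2 = 45 off-diagonal pairs if it is not collapsed. Sample Size Considerations gives a "required sample size of 33 evaluable subjects per imaging modality". With two exams each, that is 33 x 2 = 66 exams per sub-study, and 4 x 66 = 264 over sub-studies A-D. The protocol gives no figure for reader reliability, so there is no stated result to reproduce.

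**Formulas.** Bowker statistic: the sum over i<j of (n_ij - n_ji)^2 / (n_ij + n_ji), referred to chi-square. Diagonal counts n_ii do not enter. Quadratic-weighted kappa: 1 minus (observed mean squared difference) / (mean squared difference expected if the readers were independent).

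**Exact example, 64 exams, no simulation.**

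- *Pair 1, statistically independent.* Scores 6/7/8, table rows 4, 8, 4 / 8, 16, 8 / 4, 8, 4. The table is symmetric, so Bowker = 0 and p = 1. Each reader's variance is 0.5. The observed mean squared difference is 0.5 + 0.5 = 1 and the expected value is also 1, so kappa = 1 - 1/1 = 0.
- *Pair 2, perfect rank order.* Reader 1 gives 6/7/8 to 16/32/16 exams and reader 2 is always one point lower. Bowker = 16^2/16 + 32^2/32 + 16^2/16 = 64. With 3 df (non-empty pairs) p = 8.2e-14; with 45 df p = 0.033. The observed mean squared difference is 1 and the expected value is 0.5 + 0.5 + 1^2 = 2, so kappa = 1 - 1/2 = 0.50.

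The pair with no agreement passes and the pair with more agreement fails.

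**Simulation.** The protocol gives no score distribution, so four were assumed: uniform 1-10, and normal scores rounded and limited to 1-10 with (mean, SD) = (7, 1), (7, 1.5) and (6, 2). There were 4,000 runs per setting, alpha 0.05, and df equal to the number of non-empty pairs. Related readers have latent correlation 0.8. Percentage of runs in which Bowker rejects:

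| Setting | Uniform | (7, 1) | (7, 1.5) | (6, 2) |
|---|---|---|---|---|
| No shift, 33 exams, chance-only | 0.00 | 0.80 | 0.45 | 0.08 |
| No shift, 33 exams, related | 0.05 | 1.07 | 0.37 | 0.08 |
| No shift, 66 exams, chance-only | 0.18 | 1.55 | 1.15 | 0.40 |
| No shift, 66 exams, related | 0.40 | 1.92 | 1.47 | 0.75 |
| No shift, 264 exams, chance-only | 2.85 | 2.65 | 2.70 | 1.92 |
| No shift, 264 exams, related | 2.45 | 2.13 | 2.48 | 2.25 |
| Reader 2 one point lower, 66 exams, chance-only | 1.1 | 86.0 | 17.1 | 2.2 |
| Reader 2 one point lower, 66 exams, related | 19.7 | 100 | 99.3 | 67.7 |

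Weighted kappa at 66 exams is 0.00 for chance-only readers throughout. For related readers it is 0.77 / 0.73 / 0.76 / 0.78 without the shift and 0.73 / 0.50 / 0.62 / 0.69 with it. The three-reader ICC without the shift is 0.00 versus 0.77 / 0.73 / 0.76 / 0.78. Kappa and ICC separate the two kinds of reader clearly; Bowker does not, and pooling to 264 exams does not help.

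**Sensitivity.** If true quality is correlated 0.5 between a patient's two exams, related readers at 66 exams give 0.2-2.1% (no shift) and 19.4-100% (shift). With 45 df, rejection without a shift is 0.0% at 33 and 66 exams, so the result also depends on a df convention. A separate run (mean 6, SD 1.5, 33 reads, 2,000 runs) gave the same pattern: 0.4% at kappa 0.00, 0.8% at kappa 0.86, and 99.6% for closely related readers a constant point apart (kappa 0.74).

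**The case against.** The strongest objection is that nothing depends on this check. Image quality is secondary, the readers are averaged, and the equivalence test runs whatever Bowker shows. That stands, and it sets the priority. It does not make the named test suitable for its named purpose.

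Second, the protocol never says that a non-significant result will be read as reliability, and an unseen analysis plan could add an agreement measure. Both are true. However, the protocol assigns reliability to this test, and reading non-significance as reliability is the only way the test could support it. The error lies in what is stated, not in what is left out.

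Third, a constant offset is a real loss of absolute agreement, so a rejection is not empty. This is fair: in the (7, 1) setting the shift lowers kappa from 0.73 to 0.50 and Bowker rejects in every run. A significant result does point to bias. It still does not say how reliable the readers are, since it comes more readily for related readers than for unrelated ones with the same offset.

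Fourth, *systematic difference* is shorthand, because asymmetry can occur even with identical marginal distributions. The simulated rates also rest on assumed distributions and vary widely under a shift. Both points are accepted. The conclusion follows from the test's definition and the exact example, and the simulations only illustrate it.

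**Conclusion.** The concern holds. As written, the protocol would report a symmetry test as inter-reader reliability, and that result does not measure the quantity named. Under the assumed distributions without a reader shift, the rejection rate at 33 or 66 exams is about 0-2% whether weighted kappa is 0.00 or above 0.7. With a one-point shift at 66 exams it is 1-86% for chance-only readers and 20-100% for related ones, and higher for the related pair in each distribution. These percentages depend on assumptions about scores, categories and degrees of freedom; the failure to measure agreement does not.

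The point should be fixed but is low priority. It affects one descriptive result on a secondary endpoint. The SUVmax analysis, the 33 evaluable subjects and the image-quality equivalence test are untouched.

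**What to change.** Replace the McNemar-Bowker sentence in Data Analysis with an agreement measure and its 95% confidence interval, and first settle the scale, because that decides the measure:

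- If the 10 cm score is kept as a continuous measurement, use a two-way absolute-agreement ICC across the three readers.
- If it is recorded as ordinal 1-10, use quadratic-weighted kappa for each reader pair.

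The interval should allow for two exams per patient, for example by resampling patients rather than exams. Reader-pair mean differences, or Bowker if scores are ordinal, can be kept in a following sentence, described only as a check for systematic differences between readers. Describe the scale in the same way in Measurement / Instrumentation and in Data Analysis.

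The cost is a sentence or two of text and one consistent description of the scale. The readers and scores stay the same, with no further reads or patients.

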This project team has been serving as imaging core laboratory for pharmaceutical and national cooperative network groups, the CALGB/ALLIANCE since 2004 and for the SWOG NCI network group as of 2012 and has been also a performing site for the NIH ADNI multi-center trial. The team has constantly witnessed those variations in local practice that lead to many challenges, protocol deviations, and potentially higher than necessary radiation exposure from the radiotracer dosing. The Graham paper also highlighted that European dose recommendations are generally lower with approaches as low as (185 MBq [5 mCi]) for 3D acquisition in a 70 kg patient. Despite the increasing desire to reduce unnecessary medical imaging induced radiation exposure, no well-designed intra-individual crossover designed trial has been performed to generate the evidence and guiding methodological approach to resolve these issues using current state of the art PET/CT systems.

The guiding principal in radiation protection is as low as reasonably achievable (ALARA) [Hendee Sem Nucl Med 1986], but nevertheless objective evidence needs to be presented to change current standard of care practice policies or clinical trial recommendations for PET imaging pharmaceutical dosing.

Substantial research and advancements have been achieved to reduce the radiation burden from the associated CT attenuation scan, and rapid changes for the CT acquisition of the PET/CT imaging procedure are currently being implemented [Kinahan Phys Med Bio 2012].

While simulation approaches are available by segmenting list mode acquired image data to sub-samples, and while they use only PET events expected if a patient would have received a lower dose under the assumption that there is a linear physical and biological relationship in uptake at the relevant dose, this has never been systematically and prospectively validated.

Our goal is primarily to generate the evidence that ¹⁸F-FDG PET imaging can be equivalently performed at a significant lower radioactive dose than what is currently a common US standard of care dosing at 481 MBq (13 mCi). Furthermore, we want to confirm that a change in FDG uptake that might be occurring within the 20 min window between the 60 min and 75 min p.i. whole body sweep is not impacted by reducing the dose. At the same time, we will gather important insight on the observed intraindividual uptake change occurring within that 20 min window [Beaulieu JNM 2003].

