After appropriate patient consent and preparation, we will randomize the order in which the patient will receive the Standard of Care PET/CT and the Low Dose PET/CT (i.e. Standard of Care PET/CT on day 1 and Low Dose PET/CT on day 2, or vice versa). If the patient has requested to opt out of the additional whole-body sweep, the patient will be imaged at both examination days at 75 min +/- 10 min post injection. Otherwise, the patient imaging will start with the voluntary whole-body sweep at 60 min +/- 10 min, followed by the standard of care whole-body sweep at 75 min +/- 10 min.

It is well established that the image quality in patients that are classified by the WHO Body Mass Index (BMI) criteria as \Rightarrow obese (BMI \Rightarrow 30) is reduced and that longer bed volume acquisition times improves image quality [JNM Tech 2014 Sanchez-Jurado]. We will therefore increase the otherwise constant acquisition time per bed volume from 90 s to 120 s in those patients for both dose levels.

Using segmented reconstruction, we will be able to down sample the acquisition to be simulated as a 90 s acquisition for overall consistency.

As we are using four different current technology PET/CT systems, we will perform 4 sub-studies that are otherwise fully equivalent.

Sub-Study A: 481 MBq (13 mCi) ¹⁸F-FDG vs. 185 MBq (5 mCi) using Gemini Astonish PET/CT

Sub-Study B: 481 MBq (13 mCi) ¹⁸F-FDG vs. 185 MBq (5 mCi) using Biograph mCT **Sub-Study C:** 481 MBq (13 mCi) ¹⁸F-FDG vs. 185 MBq (5 mCi) using Discovery PET/CT

Sub-Study D: 481 MBq (13 mCi) ¹⁸F-FDG vs. 185 MBq (5 mCi) using Vereos 128 digital PET/CT

We are furthermore planning two additional sub-studies.

Current simulations indicate that we should be able to further reduce the FDG imaging pharmaceutical dose to an even lower level. We will determine that comparison level after completing of Sub-Study D. At this time we would assume that the clinical SOC dose would have been already reduced to 240.5 MBq (6.5 mCi), and we would then compare it to 92.5 MBq (2.5 mCi).

Sub-Study E: 241 MBq (6.5 mCi) ¹⁸F-FDG vs. 93 MBq (2.5 mCi) using Vereos 128 digital PET/CT

We plan for the possibility that one of the three-Sub-Studies (A-B) would not demonstrate equivalency, and we would then perform a modified protocol in which the SOC dosing is compared to a lower and higher dose than originally tested.

Sub-Study F: 481 MBq (13 mCi) ¹⁸F-FDG vs. tbd MBq using the system that did not show equivalency in Sub-Study A-C

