For each participant, written informed consent will be obtained prior to any protocol related activities in a private area with a study team member. As part of this procedure, study personnel will approach eligible participants and explain orally and in writing the nature, duration, and purpose of the study as well as all associated risks and benefits. They will inform the participant that he/she may withdraw from the study at any time. If the patient agrees, he/she will have additional PET acquisitions either before or after their standard of care PET imaging.

The patient will be randomized to either Group A or Group B.

Group A will receive the standard of care 13mCi injection of the radiopharmaceutical and will begin imaging at 60 minutes post-injection.

If the patient agrees, there will be two imaging sweeps 1) 60-75 minutes post-injection and 2) 75-90 minutes post-injection. The 75-90 minute post-injection acquisitions will be utilized for the standard of care diagnostic read.

After the initial scan, the patient will be scheduled for a follow-up PET/CT scan that will take place ≥ 20 hours and ≤ 2 weeks after injection. At the follow-up exam, the patient will receive a 5mCi injection of the same radiopharmaceutical and will begin imaging at 60 minutes post-injection. If the patient agrees, there will be two imaging sweeps 1) 60-75 minutes post-injection and 2) 75-90 minutes post-injection.

Group B will be identical to Group A with the exception that the first exam is performed using a 5mCi injection of the FDG radiopharmaceutical, followed by the SOC dose of 13 mCi at the second exam/

Risks:

Patients will have an additional intravenous injection of FDG at the low dose of 5/13 of the standard care dose, 5 mCi (185MBq). The radiation dose for the additional low dose FDG PET will be 4 mSv, which is equivalent to 10 month of natural radiation exposure for someone living in the USA.

There is slight risk of inflammation, infection, or hematoma from the i.v., and there is some associated discomfort. This is a standard procedure for many diagnostic tests. The i.v. will be removed prior to the

positioning of the patient within the PET scanner. There is a remote possibility of an allergic reaction to FDG, though we are unaware of any reported incidents.

Benefits:

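### The protocol gives inconsistent intervals between the two sweeps of an exam, yet Aim 2 analyses the change in SUVmax as a single 60-to-75 min interval

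*Protocol*

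**What the plan says.** The interval between the two sweeps is described in four places in the protocol.

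- **III. Background and Rationale:** uptake change "within the 20 min window between the 60 min and 75 min p.i. whole body sweep".
- **IV. Procedures, Measurement / Instrumentation:** the trial will give insight into "intra-individual variability in FDG uptake within such a 15 min +/- 10 min window".
- **IV. Procedures, Detailed study procedures:** "two imaging sweeps 1) 60-75 minutes post-injection and 2) 75-90 minutes post-injection", with no tolerance.
- **IV. Procedures, Research Design** (also I. Overview and the Figure 1 caption): "voluntary whole-body sweep at 60 min +/- 10 min, followed by the standard of care whole-body sweep at 75 min +/- 10 min".

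Research Design also raises the "acquisition time per bed volume from 90 s to 120 s in those patients for both dose levels", for patients with BMI of 30 or more. Those data can be down-sampled to a 90 s equivalent. That equalises counts but does not change the time between sweeps.

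The Data Analysis section then defines the Aim 2 variable: "The percentage of change in SUVmax measured from 60 min to 75 min will be tested first for equivalence" between the two doses. After that, SUVmax at 60 min is compared with SUVmax at 75 min within each dose. Neither comparison mentions actual start times or a permitted gap.

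**The concern.** If uptake is still changing at these times, the measured change depends on how long the gap was. The gap is therefore the time base of the Aim 2 endpoint, and the protocol does not fix it.

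Two comparisons are exposed in different ways. In the dose comparison each patient is their own control, so the threat is a gap that differs between that patient's two visits: it adds a difference unrelated to dose. In the within-dose 60-versus-75 min comparison the threat is gaps that differ between patients, including systematically by BMI. The result is then labelled a 15-min change when it may be an average over other intervals. The trial wants this figure to inform whether scanning near 75 min can stand beside the 60-min recommendation.

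**Working it through.** **1. What the stated times imply**

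| Section | Nominal gap | Permitted gap |
|---|---|---|
| Background and Rationale | 20 min | not stated |
| Measurement / Instrumentation | 15 min | 5 to 25 min |
| Detailed study procedures | 15 min | 15 min only |
| Research Design (start windows 50–70 and 65–85 min) | 75 − 60 = 15 min | 65 − 70 = −5 to 85 − 50 = 35 min, i.e. 15 ± 20 |

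The 20 min does not follow from 60 and 75. The 5 to 25 min does not follow from the two start windows. The second sweep must follow the first, so the real lower bound is the sweep duration and the upper bound is 35 min.

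**2. Bed time**

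The number of beds is not stated, so this step is conditional. Sweep length = beds × 1.5 min, or beds × 2.0 min at 120 s.

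| Beds (assumed) | 90 s | 120 s |
|---|---|---|
| 6 | 9 min | 12 min |
| 7 | 10.5 min | 14 min |
| 8 | 12 min | 16 min |
| 10 | 15 min | 20 min |

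If the 15-min slot is filled at 90 s (10 beds), the sweep takes 20 min at 120 s. After a 60-min start the second sweep cannot begin before 80 min. That breaks the 75–90 slot but stays within 75 ± 10. A first start after 65 min, still inside its own window, pushes the second past 65 + 20 = 85 min and out of its window. At 120 s, 7 beds (14 min) would still fit the slot.

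**3. Spread of gaps if the windows are used freely**

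Assumption: starts uniform and independent in the two windows, keeping only pairs in which the second sweep follows the first.

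| Sweep length | Pairs kept | Mean gap (SD) | Gap > 25 min | Gap < 15 min | A patient's two visits differ by > 5 min |
|---|---|---|---|---|---|
| 9 min | 76% | 18.5 (6.0) | 17% | 34% | 56% |
| 15 min | 50% | 21.7 (4.7) | 25% | 0% | 46% |
| 20 min | 28% | 25.0 (3.5) | 44% | 0% | 33% |

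This is what the windows permit, not a forecast of practice.

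**4. Effect on the dose comparison**

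Inputs from Sample Size Considerations: COV 12%, limit 10%, alpha 0.025, 33 evaluable patients. The plan's own figure reproduces. TOST in a two-period crossover with SE = 0.12 × √(2/33), 31 degrees of freedom and true difference 0 gives power 81.3%, and 33 is the smallest N that reaches 80%.

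For Aim 2 the variable is a log ratio within an exam, compared between two exams. With within-exam correlation ρ (not given, so assumed), baseline variance = 2 × 2(1 − ρ) × 0.12². This is 0.0288 at ρ = 0.5 and 0.00576 at ρ = 0.9. Gap mismatch adds rate² × 2 × SD(gap)². With SD 4.7 min, 2 × 4.7² = 44.2. The rate of uptake change is not in the protocol, so it is also assumed.

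| Rate per min | Added variance | Increase, ρ = 0.5 | Power, ρ = 0.5 | Increase, ρ = 0.9 | Power, ρ = 0.9 |
|---|---|---|---|---|---|
| 0 | 0 | – | 81% | – | > 99.9% |
| 0.3% | 0.0004 | 1% | 80% | 7% | > 99.9% |
| 0.6% | 0.0016 | 6% | 78% | 28% | > 99.9% |
| 1.0% | 0.0044 | 15% | 73% | 77% | > 99.9% |

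The extra variance is treated as normal noise, and the 10% limit is taken over from Aim 1. For a single patient, a 10-min mismatch between visits shifts the difference by 3, 6 or 10 percentage points at these rates.

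**5. Effect on the within-dose comparison**

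At a constant rate the estimated change scales with the mean gap. Strictly back-to-back scanning with a 15-min sweep gives 15/15, so no distortion. A 20-min sweep gives 20/15 = 1.33 in the obese patients only, so the pooled figure depends on the BMI mix.

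**The case against.** Much of the opposing case stands. Three of the four statements share a nominal 15 min. The 20 min in Background and Rationale may be a slip, because Measurement / Instrumentation uses the same phrase for the ± 10 min tolerance around 60 min. The consecutive slots can be read as the nominal schedule and the windows as its tolerance. It would go too far to call the four descriptions wholly incompatible.

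A reader might infer that gaps start at about 9 min, or alternatively that they always exceed 15 min. Neither is in the protocol. The first needs an assumed 6 beds. The second fails under that same assumption, where 34% of gaps are below 15 min.

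A reader might also take mean gaps of 21.7 and 25 min as showing that the 15-min change is overstated by 45% and 67%. Those ratios depend on independent uniform starts, with 50% and 72% of the drawn pairs discarded as impossible. One session with consecutive sweeps would give 0% and 33%.

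Nor does the 120 s bed time distort the dose comparison much. It applies to both of a patient's exams and largely cancels. Technologists are to be blinded to dose, so visit-to-visit mismatch is noise and there is no stated reason for it to favour one dose.

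Finally, handling of actual scan times may be in a statistical analysis plan that is not shown, and the protocol already accepts that opt-outs may cost Aim 2 its power. That limits the criticism of Data Analysis to its nominal definition. It does not cover the acquisition schedule, which belongs to the protocol and does not agree with itself.

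**Conclusion.** The point holds for Aim 2 as an inconsistency with a modest statistical cost. The gap is 20 min in one section and nominally 15 min in three, with a tolerance of none, ± 10 or an implied ± 20 min, and the analysis treats it as one interval.

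For the dose comparison the loss is small to moderate. With a 15-min sweep and gaps spread over the windows, power is 80%, 78% or 73% instead of 81% at ρ = 0.5, and essentially unchanged at ρ = 0.9. The rates, the correlation, the bed count and the uniform starts are all assumptions. For the within-dose comparison the size cannot be fixed from the protocol. It depends on how closely sweeps follow each other and on the share of patients scanned at 120 s per bed.

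It might be inferred that the main result or the sample size is also at risk. It is not: the primary test uses the 75-min scan alone, and N = 33 does not depend on the gap.

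**What to change.** 1. Reconcile Overview, Background and Rationale, Research Design (with the Figure 1 caption), Measurement / Instrumentation and Detailed study procedures to one statement of the two start times and the permitted gap. Say how it applies at 120 s per bed. The times are for the investigators to choose.
2. In Data Analysis, define the Aim 2 variable as the log ratio of SUVmax, second sweep over first, and adjust for the recorded start-to-start gap. For the dose comparison, the covariate is the difference in gap between the patient's two visits. For the 60-versus-75 min comparison, report the change estimated at a 15-min gap. Give the unadjusted change alongside.

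Simple division by the number of minutes should not be the required endpoint, because it weights measurement noise unequally. In the model above with a 15-min sweep and ρ = 0.5, its variance relative to the raw change (rescaled to the same mean) is 1.13, 1.08 and 0.99 at 0.3%, 0.6% and 1.0% per min. With a 9-min sweep it reaches 1.34.

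The cost is wording, the recording of each sweep's start time, one covariate (one of 31 degrees of freedom) and an assumption that log SUVmax changes roughly linearly over the short gap. If uptake changes very slowly, the adjustment gains little. No extra scans or patients are needed.
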